16.1.4 Institutional Review Board/Ethics Committee & Regulatory Authorities

Ethics Committee (EC) and Regulatory Authority approval for the study is required prior to beginning the study. A copy of the approvals must be sent to the Sponsor prior to the site initiation.

Any additional requirement imposed by the EC or regulatory authority shall be followed, as appropriate.

16.2 Sponsor Responsibilities

SafeHeal, and/or their designee, is the Sponsor of the clinical study. The Sponsor's responsibilities in the study include to:

- Provide study device to participating study sites, in quantities sufficient to support study activities.
- Provide all training to investigators and study sites staff.
- Select the Principal Investigator, all associate investigators and study sites, and other consultants, who participate in the study.
- Provide financial support to the study sites per individual contracts with each site.
- Subscribe to an insurance policy covering potential risks associated with the usage of the study device in the scope of this clinical study

SAFE-2023 Colovac 2 Study Clinical Investigation Plan

- Establish all regulatory standards per national and local regulations for clinical study sites, and other participants, and perform regular site monitoring to assure compliance with them. The ethics committee will be notified by the Study Sponsor of:
 - all unexpected serious device related adverse events (USADEs) immediately, but no later than 5 business days after the sponsor becomes aware of a new reportable event or new information related to a previously reported event.
 - all other serious device-related adverse events (SADEs) shall be reported within 10 business days after the sponsor becomes aware of a new reportable event or new information related to a previously reported event.
- Perform site monitoring of clinical data at the clinical study sites on a regular basis, retain ownership of all clinical data generated in this study and control the use of the data. SafeHeal will exercise no veto over publication of study results in the medical literature but will be provided with advance copies of manuscripts and abstracts to review for technical accuracy.
- Ensure that the study is conducted per protocol requirements. Any deviation will have to be documented as a protocol deviation on the appropriate CRF and reported per national regulations.

16.3 Monitoring

SafeHeal, as the sponsor of this study, is responsible for ensuring that adequate monitoring at each site is completed to ensure protection of the rights and safety of subject and the quality/integrity of the data collected and submitted. However, SafeHeal has transferred certain clinical investigation-related duties and functions, including monitoring, to:

Clinical Accelerator
[name]
[name]

The Monitoring visits will be conducted at the start, during and at the closure of the clinical study in accordance with a Monitoring Plan developed for this study. The Monitoring Plan includes the frequency of monitoring visits, source data verification procedures and procedures for monitoring subject compliance for this study. Monitors are appropriately trained and qualified to monitor the adherence to the investigational plan, the signed investigator agreement, compliance to the IRB/EC conditions and guidelines and compliance to applicable regulations. Any non-compliance with these items that is not adequately addressed by the principal investigator and/or his/her research site staff is cause for the Sponsor to put the investigator site/staff on hold or withdraw the investigator/site staff from participation in the study. During a monitoring visit, the monitor may review source documents and informed consents for a representative number of subjects and/or CRFs. Frequency of monitoring visits will be based upon enrollment, study duration, compliance and any suspected inconsistency in data that requires investigation. In between monitoring visits, the monitors will maintain personal contact with the Principal Investigator and staff throughout the study by phone and/or e-mail on a regular basis.

SAFE-2023 Colovac 2 Study Clinical Investigation Plan

16.4 ISO 14155 Compliance

This clinical study will be conducted in accordance with the standard EN ISO 14155:2020 and the recommendations guiding physicians in biomedical research involving human subjects adopted by the World Medical Assembly, Helsinki, Finland, 2013 and later revisions.

SAFE-2023 Colovac 2 Study Clinical Investigation Plan

17.0 Revision History

Ver.	Change	Date
0	Original Issue	15 Aug 2023
1	
 Modified Inclusion criterion 2 to restrict population to subjects with planned diverting loop ileostomy for malignancy, based on multidisciplinary team recommendations. Modified Exclusion criterion 5a to better define metastatic disease Added Exclusion criterion 6 f) to restrict population to subjects with an anastomosis within 15 cm of anal verge. Updated Colovac 2 and SmartVac device descriptions Added Staff Ease of Device Use, Subject Tolerance and Ease of Use of Device, and Retrieval Usability Questionnaires Increased frequency of CRP and WBC collection from every 2 days to daily during hospitalization 	12 Apr 2024
2	
 Added endoscopic evaluation of the mucosa at the 1-month visit Updated investigational device management to include CRO and align with Device Management Plan Added ISREC grading of anastomotic leaks Updated safety assessment and reporting to align with Safety Management Plan 	12 Sep 2024

19.0 Abbreviations

Abbreviation/Term	Definition
AE	Adverse Event
AL	Anastomotic leakage
BBPS	Boston Bowel Preparation Scale
CRP	C-Reactive Protein
CT	Computed Tomography
EC	Ethics Committee
ECOG	Eastern Cooperative Oncology Group
eCRF	Electronic Case Report Form
EU	European
FDA	Food and Drug Administration
GDPR	General Data Protection Regulation
ICF	Informed Consent Form
IDE	Investigational device exemption
IFU	Device Instructions for Use
IRB	Institutional review board
ISREC	International Study Group of Rectal Cancer
OUS	Outside of the United States
PI	Principal Investigator
QOL	Quality of life
SADE	Serious Adverse Device Events
SAE	Serious Adverse Event
TME	Total Mesorectal Excision
UADE	Unanticipated adverse device effect
USADE	Unanticipated Serious Device Adverse Effect
US	United States
WBC	White Blood Cell

SAFE-2023 Colovac 2 Study Clinical Investigation Plan

20.0 Appendices

- Appendix 1: ECOG Performance Status Score
- Appendix 2: Boston Bowel Preparation Scale score
- Appendix 3: ISREC grading

SAFE-2023 Colovac 2 Study
Clinical Investigation Plan

20.1 Appendix 1: ECOG Performance Status Score

ECOG Performance Status Scale

GRADE	ECOG PERFORMANCE STATUS
0	Fully active, able to carry on all pre-disease performance without restriction
1	Restricted in physically strenuous activity but ambulatory and able to carry out work of a light or sedentary nature, e.g., light house work, office work
2	Ambulatory and capable of all selfcare but unable to carry out any work activities; up and about more than 50% of waking hours
3	Capable of only limited selfcare; confined to bed or chair more than 50% of waking hours
4	Completely disabled; cannot carry on any selfcare; totally confined to bed or chair
5	Dead

SAFE-2023 Colovac 2 Study Clinical Investigation Plan

20.1 Appendix 2: Boston Bowel Preparation Scale (BBPS)

Diversion of the fecal stream will be assessed using the BBPS score below:

BBPS Score	Description
0	Unprepared colon segment with mucosa not seen due to solid stool that cannot be cleared.
1	Portion of mucosa of the colon segment seen, but other areas of the colon segment not well seen due to staining, residual stool and/or opaque liquid.
2	Minor amount of residual staining, small fragments of stool and/or opaque liquid, but mucosa of colon segment seen well.
3	Entire mucosa of colon segment seen well with no residual staining, small fragments of stool or opaque liquid.

SAFE-2023 Colovac 2 Study Clinical Investigation Plan

SAFE-2023 Colovac 2 Study Clinical Investigation Plan

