9.4 Primary Objective

SAFE-2023 Colovac 2 Study Clinical Investigation Plan

The primary study objective is to evaluate the clinically significant (CS) migration rate of the Colovac 2 device during its 10-day implantation period.

9.5 Primary Performance Endpoint at Day 10

The primary performance endpoint is the clinically significant migration rate of the Colovac 2 device during its 10-day implantation period.

Clinically significant migration is defined as movement of device that allows fecal contents to reach the anastomosis site evidenced by:

- Migration of entire stent to or below the Sacral Promontory as indicated by fluctuation in the length of the sheath that extends out of the anus and confirmed by radiographic displacement, with or without subject symptoms or clinical findings suggestive of anastomotic leak (pain, fever, elevated CRP, elevated WBC); or
- Expulsion of the device.

9.6 Secondary Objectives:

The secondary objectives of this study are to assess the:

- Preliminary safety and performance of the Colovac 2 System
- Ease of use of the Colovac 2 Colorectal Anastomosis Protection Device
- Ease of use of the Colovac 2 Introducer and Implant and Vacuum Management Device

9.7 Other Performance Endpoints at Day 10

The other performance endpoints are:

- Ostomy avoidance rate
- Cleanliness of colon immediately prior to device retrieval
- Staff Ease of Use of Device
- Subject Tolerance and Ease of Use of Device

9.8 Safety Endpoints at Day 10

The safety endpoints are:

- Mucosal appearance at anchoring site after device removal
- Device related complications
- All complications

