1. Colonoscopy will be performed prior to the device retrieval, between the colon wall and the sheath, to assess visually the presence of feces (sealing function integrity of the Colovac 2 device) and the integrity of the anastomosis. The Boston Bowel Preparation Scale (BBPS, see Appendix 2) score will be assessed by an independent reviewer (CEC). Still images of the anastomosis will be captured during the procedure and the pseudonymized images should be sent on a secure platform for analysis, and anastomosis healing and signs of leak will be assessed by an independent reviewer (CEC).
2. Device retrieval - Please refer to the Instructions for use of the Colovac 2 Device for retrieval instructions.
3. Endoscopic evaluation after device retrieval

An endoscopic evaluation with video will be performed immediately after retrieval of the Colovac 2 Device to check for colonic wall injury at the anchoring site and to evaluate anastomotic integrity. The pseudonymized imaging should be uploaded on a secure platform for analysis. These will be

SAFE-2023 Colovac 2 Study Clinical Investigation Plan

analyzed by an independent reviewer (CEC) to determine vessel impact, with an assessment of mucosal appearance by grading bleeding, perforation and ulceration. If ulceration is present, percentage of ulceration will also be assessed.

After retrieval of the Colovac 2 Device, the anastomosis will be evaluated.

If an anastomotic defect is identified, treatment will be at the surgeon's discretion. Anastomotic defects/leaks may be treated with antibiotics only, and/or by percutaneous drainage, and/or surgically (revision of the anastomosis, repair of the anastomotic defect, stoma creation).

Handling of anastomotic complications during the implantation period

Any subject presenting with clinical signs suggestive of anastomotic leakage observed during the implantation period of the Colovac 2 Device will be treated as per standard clinical practice.

Subjects with clinical signs or symptoms of anastomotic leakage will undergo CT scan. Definitive treatment of anastomotic leakage will be per the treating surgeon's discretion and based on the severity of the clinical symptoms and radiological findings. Treatment may consist of antibiotics only, and/or percutaneous drainage, and/or reoperation.

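### Fecal diversion is scored with a bowel-preparation visibility scale, with no rule that scoring precedes washing and no defined result for the direct check for feces

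*Combined protocol and SAP*

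**What the plan says.** Section 9.7 lists "Cleanliness of colon immediately prior to device retrieval" among the other performance endpoints at Day 10. Appendix 2 names the instrument: "Diversion of the fecal stream will be assessed using the BBPS score below". Its anchors are:

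- Score 0: "Unprepared colon segment with mucosa not seen due to solid stool that cannot be cleared".
- Score 1: part of the mucosa is seen, with "other areas of the colon segment not well seen due to staining, residual stool and/or opaque liquid".
- Score 2: "Minor amount of residual staining, small fragments of stool and/or opaque liquid, but mucosa of colon segment seen well".
- Score 3: "Entire mucosa of colon segment seen well with no residual staining, small fragments of stool or opaque liquid".

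Section 11.3, first step of device retrieval, has a colonoscopy pass between the colon wall and the sheath before the device is removed. Its stated purpose is "to assess visually the presence of feces (sealing function integrity of the Colovac 2 device) and the integrity of the anastomosis". Stills of the anastomosis are taken at some point in that session, and an independent CEC reader assigns the BBPS. Section 14.3 lists what the CEC assesses. BBPS and anastomosis healing are on the list; presence of feces is not. Section 13.0 and the synopsis leave analysis definitions to a separate SAP, and section 14.3 refers to a CEC Charter. Neither text is in the supplied document.

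**The concern.** The question at this colonoscopy is whether feces got past the seal and reached the anastomosis. For that question, stool lying outside the sheath is the finding, whether or not it can be washed away. The BBPS asks instead how well the bowel wall can be inspected, and on that question stool that can be removed matters little. The same session must also inspect the anastomosis, which gives an endoscopist a reason to clear the field before taking the picture.

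At stake is the interpretation of the one listed endpoint aimed at sealing. If residue can pass as cleanliness, a favourable cleanliness rate would not show that the sheath kept feces off the anastomosis.

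**Working it through.** The plan attaches no threshold, target rate or sample-size argument to this endpoint, so the check is mainly a reading of the anchors against their stated use.

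**Step 1. What the anchors can register.** If residue is visible when the score is given, the segment cannot score 3. Stool or liquid hiding part of the mucosa gives 1. Fragments or opaque liquid with mucosa well seen give 2. Stool that hides all of the mucosa but can be cleared fits no anchor as first seen: 0 requires that it cannot be cleared, and 1 requires that part of the mucosa is visible. The wording of score 0 therefore presupposes some attempt at clearing before the score is given. That is an inference from the anchor; 11.3 describes no such step.

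**Step 2. When soiling would pass as clean.** Two choices decide this: when the score is taken, and which scores count as clean.

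| | Clean = 3 only | Clean = 2 or 3 |
|---|---|---|
| Scored at first view | No visible residue passes | Fragments or opaque liquid pass |
| Scored after clearing | Stool that was fully cleared passes | Stool that was fully or mostly cleared passes |

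Only the upper left cell protects the endpoint. Section 9.7 fixes that the assessment comes before retrieval, not that it comes before washing. Neither 9.7, 11.3 nor Appendix 2 states a cut-off, mentions irrigation or suction, or says which segment is scored. The endpoint speaks of the colon, while the stills are of the anastomosis.

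**Step 3. Whether another endpoint would catch a leaking seal.** The primary endpoint in 9.5 speaks of device movement that lets feces reach the anastomosis, but it is evidenced only by stent position (sheath length with radiographic confirmation) or expulsion. A seal that leaks while the stent stays in place is not counted. The remaining items in 9.7 concern ostomy avoidance, ease of use and tolerance. The visual check for feces in 11.3 would answer the question directly, but it has no endpoint in 9.7, no entry in the CEC list in 14.3, and no line of its own in the schedule of procedures (Table 3), which names only the BBPS score with still images.

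**Step 4. Size.** With n subjects scored, each subject read as clean instead of soiled moves the rate by 1/n. At the maximum enrolment of 50 this is 1/50 = 2 percentage points per subject. The documents give no figure for how many segments might carry clearable stool or score 2, so this cannot be turned into an estimate. The earlier clean-anastomosis rates of 87% (section 4.2) and 92% (section 4.3) do not help: neither section defines clean or names the scale. They show only that cleanliness has been reported before as a single percentage, which is why an unstated cut-off matters.

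**The case against.** The strongest reply is that the scale does register soiling. Score 3 excludes all visible residue and score 1 captures stool that obscures the wall. Section 13.0 calls for the number and percent in each category of a categorical variable, so a reader could see how many segments scored 2. Section 11.3 already has the endoscopist look for feces, and names this ahead of anastomotic integrity. A cut-off or reading convention may be in the SAP or the CEC Charter. The endpoint is non-primary and descriptive, in a single-arm study that calls its own assessment preliminary.

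Most of this stands, and it limits the point. A reader might infer that a failed seal will be scored as a success whenever the stool can be cleared, or that the endpoint is biased towards good performance. The documents do not support either statement, because no washing step and no clean cut-off are written down.

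Two things survive. A table of score categories exposes score 2 but cannot show stool that was removed before the image was taken. Nor can an analysis rule in a SAP recover that state afterwards. A Charter could contain an acquisition rule, but the sites take their images under section 11.3. The direct observation is planned, yet it is given no result that would be reported.

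**Conclusion.** The concern holds in a limited form. A visibility scale is named as the measure of diversion, the timing of scoring relative to clearing is not fixed, and the more direct finding has no defined result. Misreading of soiling as cleanliness is possible under three of the four combinations in the table. That count is not a probability, since the documents do not say which combination applies.

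The effect is confined to one descriptive endpoint. The primary migration endpoint does not use the BBPS, and no hypothesis or target rate rests on cleanliness. The size cannot be estimated from the documents. The conclusion assumes that the unseen SAP and CEC Charter do not already require a pre-wash image and name the score that counts as clean. If they do, what remains is to bring those rules into 11.3 and to give the feces check a reported result.

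The change is still worth making, because a more direct measure is available from a colonoscopy, images and a reader that are already planned.

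**What to change.** 1. In section 11.3, first retrieval step, and in Appendix 2, require that the still image used for scoring is taken at first view of the anastomotic segment, before any irrigation or suction. Later washing and inspection are unaffected.
2. In section 9.7, report *feces at the anastomosis before washing (yes/no)*, read by the CEC, as the sealing result. Add it to the CEC's list in section 14.3.
3. Keep the BBPS as supporting description and report its full 0 to 3 distribution. If a single clean percentage is also given, state in advance which scores it includes.
4. Apply the rule to subjects whose device has not yet been retrieved. Report separately any already retrieved subjects without a documented pre-wash image. Section 9.2 dates first enrolment to July 31, 2024, so there may be some.

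The cost is wording in these sections and one added data field, with no added procedure or reader. There are two downsides: the reported cleanliness rate may be less favourable, and the sealing result may be missing for early subjects.

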20.2 Appendix 3: ISREC Grade

Anastomotic leaks will be graded according to the ISREC grading system that classifies ALs into one of three grades based on severity and required treatment. The ISREC grades are defined as follows:

- Grade A anastomotic leakage is identified by radiographic findings of a perianastomotic fluid collection, leakage of contrast through the anastomosis, or observation of new drainage of enteric contents through either a drain or through a fistula but without accompanying clinical complaints. These may be managed expectantly. These may become apparent during the preoperative work-up prior to closure of a diverting ostomy and will at least delay reversal.
- Grade B anastomotic leakage requires therapeutic intervention but does not necessarily require reoperation. Antibiotics and percutaneous drainage of fluid collections are the most common nonoperative interventions.
- Grade C anastomotic leakage requires repeat laparotomy. Surgical treatment is performed with the goal of controlling life-threatening sepsis. The traditional operation with takedown of the anastomosis and end colostomy may be appropriate, but washout with drain placement and diverting loop ileostomy may also be appropriate.
